#### Apixaban NON-INTERVENTIONAL STUDY PROTOCOL

- 4. Compare the risk of death among elderly patients treated versus untreated with OACs in the Medicare NVAF population.
- 5. Compare the all-cause health care costs among elderly patients treated versus untreated with OACs in the Medicare NVAF population.

**Study Design:** The study will be a longitudinal retrospective cohort analysis using the US Centers for Medicare & Medicaid Services (CMS) Medicare dataset from 01JAN2012-31DEC2016. The study will designate a 12-month baseline period prior to the identification period (01JAN2013-31DEC2016). This database only includes patients enrolled in fee-for-service (FFS) Medicare; those enrolled in managed-care plans will be excluded. Further, patient eligibility will be based on selection from the database according to the following inclusion and exclusion criteria (sections 2).

**Population:** Elderly patients (aged  $\geq 65$  years) will be required to have  $\geq 1$  inpatient or  $\geq 2$  outpatient medical claims (the 2 outpatient claims are  $\geq 7$  days apart) for AF during the identification period for the primary and secondary objectives. For the primary objective, two mutually-exclusive NVAF patient cohorts will be created: ever-treated with OAC and never-treated with OAC. For the secondary objective assessing clinical and healthcare utilization and costs, treatment status will be a time-varying covariate and ever-treated patients will contribute time-not-on-treatment to untreated effect.

For the primary and secondary objectives, the ever-treated with OAC population cohort will include newly diagnosed NVAF patients who ever initiated oral anticoagulant (OAC) treatment (apixaban, dabigatran, edoxaban, rivaroxaban, and warfarin) during the study period identified from 01JAN2013-31DEC2016. The never-treated with OAC population cohort will include newly diagnosed NVAF patients without any OAC claim from 01JAN2013-31DEC2016.

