For the primary and secondary objectives, the first AF diagnosis date during the identification period will be used as the index date for both ever-treated and never-treated cohorts. Across both ever-treated and never-treated cohorts, all patients will be required to have a  $CHA_2DS_2$ -VASc $\geq 2$  and 12-months of continuous health plan enrollment, with medical and pharmacy benefits before the index date (baseline period). For the primary objective and high-risk subgroup analyses, patients will also be required to have 6-month continuous health plan enrollment, with medical and pharmacy benefits after the index date.

For the primary objective and high-risk subgroup analyses, the following patients will be excluded: an AF diagnosis any time prior to the first AF diagnosis; medical claims indicating a diagnosis or procedure for mitral valvular heart disease or heart valve replacement/transplant;

Do not distribute for purposes outside of specific activities related to development of FDAMAs114 compliant pieces. Content within this protocol is subject to change based on communication planning and input by external review committees.

Apixaban NON-INTERVENTIONAL STUDY PROTOCOL

or use of OACs during the baseline period. For the secondary objective assessing effectiveness, safety, and cost outcomes, patients will be further excluded if they had any of the following: venous thromboembolism; transient AF during the baseline period; pregnancy during the study period; hip/knee replacement surgery within 6 weeks pre-index date; or follow-up period = 0 day. In addition, among patients ever treated with an OAC, those with >1 OAC prescription claim at the index date will be excluded as well.

**Variables:** Baseline demographic and clinical characteristics will include age, gender, race, geographic region, Medicaid dual eligibility, Part-D low income subsidy, Charlson comorbidity index (CCI), CHADS2, CHA2DS2-VASc, HAS-BLED scores, prior bleeding/stroke events, congestive heart failure, diabetes, hypertension, chronic obstructive pulmonary disease, renal disease, myocardial infarction, dyspepsia or stomach discomfort, peripheral arterial disease, transient ischemic attack, coronary artery disease, history of falls, medication use, and index dose of DOAC. Baseline all-cause health care costs and utilization will be included.

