# 8. Research Methods

# 8.1. Study Design

The study will be a longitudinal retrospective cohort analysis using the US fee-for-service (FFS) Medicare database. This database contains data from inpatient departments, outpatient departments, carrier claims, reported drug events, and beneficiaries' enrollment data. The following will be determined and compared between treatment status (treated with apixaban, dabigatran, edoxaban, rivaroxaban, or warfarin and untreated with OAC): outcomes including major bleeding, stroke/SE, and death; and health care costs and resource utilization. The overall study period will be from 01JAN2012-31DEC2016. The study will designate a 12-month baseline period prior to an index identification period (01JAN2013-31DEC2016). The date of first AF diagnosis during the study period will be assigned as the index date.

Figure 1. Study Periods for Primary and High-Risk Subgroup Objectives

(for illustration purposes only, may not be proportional)

Do not distribute for purposes outside of specific activities related to development of FDAMAs114 compliant pieces. Content within this protocol is subject to change based on communication planning and input by external review committees.

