## 8.2.1.2. Exclusion Criteria

- 1) Exclude patients with AF diagnosis prior to the index date;
- 2) Exclude patients with medical claims indicating diagnosis of mitral valvular heart disease or valve replacement procedure (see Appendix) during the 12 months prior to or on the index date;
- 3) Exclude patients who had a pharmacy claim for apixaban, dabigatran, edoxaban, rivaroxaban, or warfarin during the 12 months pre-index period.

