# 8.2.3. Cohorts

Patients eligible according to the above criteria will be assigned to the following cohorts:

Do not distribute for purposes outside of specific activities related to development of FDAMAs114 compliant pieces. Content within this protocol is subject to change based on communication planning and input by external review committees.

Apixaban NON-INTERVENTIONAL STUDY PROTOCOL

- 1) Ever-Treated Cohort: NVAF Patients had ≥1 pharmacy claim for apixaban, dabigatran, edoxaban, rivaroxaban, or warfarin from 01JAN2013-31DEC2016 on or after the first AF diagnosis
  - a. Apixaban cohort: Patients who initiated with apixaban on or after index date
  - b. Dabigatran cohort: Patients who initiated with dabigatran on or after index date
  - c. **Edoxaban cohort:** Patients who initiated with edoxaban on or after index date. Given the small sample size, edoxaban patients will not be included in the secondary clinical and healthcare utilization and costs analyses.
  - d. Rivaroxaban cohort: Patients who initiated with rivaroxaban on or after index date
  - e. Warfarin cohort: Patients who initiated with warfarin on or after index date
- 2) Never-Treated Cohort: NVAF patients with no pharmacy claim for an OAC from 01JAN2013-31DEC2016

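### Never-treated status is tied to a fixed calendar window rather than to the index date, so patients with an OAC claim from 2013 onward but before the 12-month washout are kept only if treated after diagnosis

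*Protocol*

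**What the plan says.** Four rules of the protocol act together.

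- **Index date.** Abstract, Population: "the first AF diagnosis date during the identification period will be used as the index date for both ever-treated and never-treated cohorts".
- **Washout.** Section 8.2.1.2, exclusion 3, applies to everyone: "Exclude patients who had a pharmacy claim for apixaban, dabigatran, edoxaban, rivaroxaban, or warfarin during the 12 months pre-index period". It moves with each patient's own index date.
- **Ever-treated.** Section 8.2.3 requires at least one claim for a listed OAC "from 01JAN2013-31DEC2016 on or after the first AF diagnosis". This is anchored to the index date.
- **Never-treated.** Section 8.2.3: "Never-Treated Cohort: NVAF patients with no pharmacy claim for an OAC from 01JAN2013-31DEC2016". The abstract agrees: "newly diagnosed NVAF patients without any OAC claim from 01JAN2013-31DEC2016". Neither is anchored to the index date.

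The data window is wider than the never-treated window. Section 8.1: "The overall study period will be from 01JAN2012-31DEC2016". The abstract describes the two cohorts as mutually exclusive, and Section 8.2.3 says that patients who meet the criteria will be assigned to them. The abstract's ever-treated wording refers to starting an OAC within the same calendar window but does not say that the start must follow the AF diagnosis.

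**The concern.** The never-treated definition looks back before the index date, and further back than the washout, for any patient indexed late enough. The ever-treated definition does not. The same old claim is therefore disregarded in a patient who later fills an OAC, but disqualifies a patient who does not.

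The primary objective is to estimate how many patients are treated and to identify what predicts treatment. A rule that keeps or drops patients according to whether they are treated after diagnosis selects on that outcome. Three things follow:

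- The ever-treated share is biased in one direction, upward.
- Within the affected stratum the treated share is 100% by construction, so characteristics that go with past OAC use look more predictive of treatment than they are.
- The disqualifying look-back lengthens with calendar time, and index year is a potential predictor in Table 1, so part of any rise in treatment over the years may be an artefact.

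**Working it through.** No figure in the protocol depends on this point, so there is nothing to reproduce first. The check applies the stated rules to example patients and then sizes the effect.

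**1. Applying the rules (12 months taken as 365 days)**

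| Index date | OAC claims | Caught by washout? | Cohort under Section 8.2.3 |
|---|---|---|---|
| 01JUL2015 | March 2013 only | No | Neither |
| 01JUL2015 | March 2013 and September 2015 | No | Ever-treated |
| 01JUL2015 | June 2012 only | No | Never-treated |
| 01OCT2013 | March 2012 only | No | Never-treated |

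The first two patients have the same history and differ only in treatment after diagnosis; one is kept and the other is lost. The last two show the limit of the problem: a 2012 claim bars nobody, because the never-treated window opens on 01JAN2013. On the abstract's looser ever-treated wording the first patient could even be counted as ever-treated, so the abstract and Section 8.2.3 can classify the same person differently.

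**2. Length of the one-sided look-back**

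This runs from 01JAN2013 to the index date minus 12 months, and is zero if negative. Section 8.2.1.1 requires 6 months of enrollment after index and the data end on 31DEC2016, so index dates for the primary objective stop at about 30JUN2016.

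| Index year | Extra look-back | Mean, dates spread evenly |
|---|---|---|
| 2013 | 0 | 0 |
| 2014 | 0-12 months | 6 months (0.5 y) |
| 2015 | 12-24 months | 18 months (1.5 y) |
| 2016 | 24-30 months | 27 months (2.25 y) |

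**3. Effect on the index-year odds ratio**

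Let N1 be the number treated, N0 the number untreated, and q the share of the *untreated* who have a claim in the look-back. The rule turns N0 into N0(1-q), so the odds of treatment become N1/[N0(1-q)], which is the true odds times 1/(1-q). There is no such loss for 2013, so this factor is also the spurious odds ratio against 2013.

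Assumption, not in the protocol: q accrues at 0.5-2% per look-back year.

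- 2014: q = 0.5 × (0.5 to 2%) = 0.25-1%; factor 1.003-1.010
- 2015: q = 1.5 × (0.5 to 2%) = 0.75-3%; factor 1.008-1.031
- 2016: q = 2.25 × (0.5 to 2%) = 1.125-4.5%; factor 1/0.98875 = 1.011 to 1/0.955 = 1.047

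**4. Effect on the ever-treated share**

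Let p be the true share, x the share of eligible patients with such a claim, and r the share of those who are treated later. The dropped fraction is d = x(1-r), and the observed share is p/(1-d). Assumptions, again not in the protocol: x = 1-5%, r = 30-70%, p = 40-60%.

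- Smallest: d = 0.01 × 0.3 = 0.003; 0.40/0.997 = 0.4012, or +0.1 percentage points
- Largest: d = 0.05 × 0.7 = 0.035; 0.60/0.965 = 0.6218, or +2.2 percentage points

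**5. After the change**

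If never-treated means no claim from the index date to 31DEC2016, the extra look-back is 0 for every index date. The first example patient moves from neither cohort to never-treated, and every eligible patient falls in exactly one cohort.

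**The case against.** The strongest reply is that the group is narrow and the effect small. Exclusion 1 of Section 8.2.1.2 removes anyone with an earlier AF diagnosis, so those affected took an OAC without recorded AF, had no claim for at least 12 months, were then diagnosed, and never restarted. Only 12 months of enrollment before index is required, so older Part D claims will not be observable for everyone. OAC use before the baseline year is not a listed predictor, so it reaches the models only indirectly. All of this stands, and it limits the size. It does not remove the selection or change its direction. Nor is the group empty by design: the exclusions for VTE and for hip or knee replacement in Section 8.2.2.2 apply only to the secondary objectives.

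One could also say that never-treated is meant to denote OAC-naive patients. If so, naivety has to be required of both cohorts as an eligibility rule; the protocol requires it of one.

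Three stronger readings are tempting but not supported:

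- *Any claim older than 12 months disqualifies an untreated patient, so all remote users in the sample are treated.* This fails for 2012 claims, which disqualify nobody. The 100% figure holds only for claims dated 01JAN2013 or later.
- *The look-back for 2016 extends to 36 months.* The 6-month post-index enrollment rule stops it at about 30 months for the primary objective.
- *Secondary objectives 2-5 are biased too.* Section 8.7 does use never-treated patients as the propensity-score reference. But treatment is time-varying, ever-treated patients also contribute untreated time, and those objectives are optional. Neither the direction nor the size of any bias in a hazard ratio or cost can be shown from the protocol.

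**Conclusion.** The point holds as a defect in the primary cohort definition. For index dates from 2014 on, an eligible patient with an OAC claim dated 01JAN2013 or later and before the washout year is retained only if treated after diagnosis, and nothing elsewhere in the protocol corrects this. The direction is certain: only patients untreated after diagnosis are lost, so the treated share can only be overstated.

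The size is probably modest and cannot be derived from the document. It is about 1.01-1.05 on the 2016-versus-2013 odds ratio if 0.5-2% of untreated patients acquire such a claim per look-back year, and about 0.1-2.2 percentage points on the ever-treated share under the ranges in step 4. Nothing here shows that a primary conclusion would reverse. The case for correcting it is that the rule selects on the primary outcome and that removing it costs almost nothing.

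**What to change.** In Section 8.2.3 and in the abstract, define never-treated as no OAC pharmacy claim from the index date through 31DEC2016, and keep the 12-month washout of Section 8.2.1.2 as the single pre-index rule for both cohorts. The check should run to 31DEC2016 and not to the end of each patient's follow-up. Ever-treated status runs to that date, so with a shorter check a patient who disenrolls, returns and then fills an OAC could meet both definitions.

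In the abstract, also state that the OAC claim defining ever-treated must fall on or after the AF diagnosis, so that it agrees with Section 8.2.3.

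If a longer OAC-free period is wanted, write it as one pre-index exclusion applied identically to both cohorts. Data begin on 01JAN2012, so the earliest index dates have only about 12 months of history and a longer period could not be observed in full for them.

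The cost is a sentence in each place and one line of cohort-selection code. No new data are needed, and the never-treated count rises slightly.

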# 8.2. Setting

Ever treated with OAC and never treated with OAC patients will be selected from 01JAN2013-31DEC2016. To ensure access to the patients' complete medical history, they will be required to have continuous health plan enrollment for the 12 months before the first AF diagnosis date/index date (baseline period). Patient data will be assessed from index date until the earliest of death, health plan disenrollment, treatment switch (treated patients), discontinuation (treated patients), or 31DEC2016 (end of study).

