# 8.2.1. Primary Objective and High-Risk Subgroup Analyses

# 8.2.1.1. Inclusion Criteria

Patients had ≥1 inpatient claim or ≥2 outpatient claims (at least 7 days gap between the two outpatient claims) for AF (ICD-9-CM code 427.31; ICD-10-CM: I480-I482, I4891) during 01JAN2013-31DEC2016. The first AF diagnosis claim dates during the identification period will be designated as the index date;

Note: Revised from  $\geq 1$  AF diagnoses based on literature review and clinical rationale to consolidate the diagnosis of AF.

2) Patients had 12-month continuous health plan enrollment with medical and pharmacy benefits (Medicare Part A, B, and D) before the index date and 6-month continuous health

Do not distribute for purposes outside of specific activities related to development of FDAMAs114 compliant pieces. Content within this protocol is subject to change based on communication planning and input by external review committees.

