#### Apixaban

NON-INTERVENTIONAL STUDY PROTOCOL

plan enrollment with medical and pharmacy benefits (Medicare parts A, B, and D) after the index date;

Note: Revised from no requirement for continuous health plan enrollment post-index date to generate comparable cohorts.

- 3) Patients had CHA2DS2-VASc score  $\geq$ 2 during 12 months on or before the index date;
- 4) Aged  $\geq 65$  years on the index date.

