#### Apixaban

NON-INTERVENTIONAL	STUDY DDOTOCOL
NON-INTERVENTIONAL	STUDIIKUIUCUL

Variable a	Role	Operational definition	
Index year	Baseline characteristic and potential predictor	A flag will be created for patients with index date in the year of 2013-2016.	
Medicaid dual eligibility	Baseline characteristic and potential predictor	A flag will be created for patients with Medicaid dual eligibility.	
Part-D low income subsidy	Baseline characteristic and potential predictor	A flag will be created for patients with a Part-D low income subsidy.	
Baseline Deyo-Charlson comorbidity index score	Baseline characteristic and potential predictor	The Deyo-Charlson comorbidity index score will be created during the baseline.	
Baseline CHADS2 score	Baseline characteristic and potential predictor	The CHADS 2 score will be used to analyze the effect of stroke risk stratification on OAC use. The maximum score is 6. CHADS 2 scores: 2-3, 4-5, and $\geq 6$ .	
Baseline CHA2DS2-VASc score	Baseline characteristic and potential predictor	The CHADS 2 VASc score will also be used as indicated above. The maximum score is 9. CHADS 2 -VASc scores: 2-3, 4-5, and $\geq 6$ .	
HAS-BLED score	Baseline characteristic and potential predictor	The HAS-BLED score will be used to estimate the risk of major bleeding. As the INR value is not available in the databases, a modified HAS-BLED score was calculated with a range of 0 to 8.	
Baseline prior bleed	Baseline characteristic and potential predictor	A flag will be created for patients with a bleeding- related claim during the baseline period.	
Baseline prior stroke/SE	Baseline characteristic and potential predictor	A flag will be created for patients with a stroke/SE claim during the baseline period.	
Obesity	Baseline characteristic and potential predictor	A flag will be created for patients with obesity claims during the baseline.	

Do not distribute for purposes outside of specific activities related to development of FDAMAs114 compliant pieces. Content within this protocol is subject to change based on communication planning and input by external review committees.

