# Logistic Regression: Predictors for OAC Treatment/non-treatment (Primary Objectives)

A logistic regression will be used to examine risk factors associated with OAC treatment (OAC, DOAC, or warfarin)/non-treatment with OACs and DOAC treatment/warfarin treatment. Predictor data will be examined during the 12 months baseline period before the index date.

Stepwise model selection will be used to identify risk factors. The final covariate lists will be finalized based on clinical rationale and model fitting.

Odds ratios, p-values, and 95% confidence intervals (CIs) for all model covariates will be provided. Diagnostic tests will be performed for the multivariate models. Hosmer-Lemeshow tests will be performed and the area under the Receiver Operating Characteristic curve will be checked.

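### The primary ever/never-treated classification has no time horizon: patients have from about 6 months to 4 years to qualify as treated, which distorts the percentages and the index-year odds ratio

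*Protocol*

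**What the plan says.** Section 8.2.3 defines the never-treated cohort as "NVAF patients with no pharmacy claim for an OAC from 01JAN2013-31DEC2016" and the ever-treated cohort as "NVAF Patients had ≥1 pharmacy claim for apixaban, dabigatran, edoxaban, rivaroxaban, or warfarin from 01JAN2013-31DEC2016 on or after the first AF diagnosis". The Abstract uses the same calendar limits. On the start of observation, section 8.2.1.1 states: "The first AF diagnosis claim dates during the identification period will be designated as the index date". On its end, section 8.2 states: "Patient data will be assessed from index date until the earliest of death, health plan disenrollment", or 31 December 2016; switch and discontinuation also end observation, but only for patients already treated.

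For the primary objective the Abstract adds that "patients will also be required to have 6-month continuous health plan enrollment" after index. Section 8.2.1.1 repeats this and notes that the rule was added to make the cohorts comparable. Neither place limits the search for an OAC claim to those 6 months.

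The primary analysis in section 8.7 reads: "A logistic regression will be used to examine risk factors associated with OAC treatment". Covariates are chosen stepwise and then settled on clinical rationale and model fit. No time at risk, censoring or fixed horizon is stated. Index year is among the candidate predictors in Table 1: "A flag will be created for patients with index date in the year of 2013-2016".

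Section 8.8 plans censoring at 6 months and a competing-risk analysis for death, both for the secondary clinical objectives only.

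**The concern.** A binary outcome that can occur at any time up to a fixed calendar date depends on how long each patient is watched. Someone indexed in January 2013 has 4 years in which to fill an OAC; someone indexed around July 2016 has 6 months. If some patients start after month 6, the earlier patient is more likely to be classed as ever-treated even when both start at the same rate.

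Two results of the primary objective are exposed. The percentages treated and never treated average over very unequal windows and answer no question with a stated horizon. The index-year odds ratio, reported as a predictor, combines any real change in prescribing with the shrinking window. To a lesser degree, predictors of death or disenrollment after month 6 shorten the window and drift toward non-treatment. The age and CHA₂DS₂-VASc subgroup analyses inherit this. Section 8.7 also makes secondary objectives 2-5 depend on how strong the predictors from this model prove to be.

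**Working it through.** The protocol gives no figure to reproduce here: its power calculation covers secondary objectives only.

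**Window, from the protocol's dates.** 01JAN2013 to 31DEC2016 is 4.0 years. An index date around 01JUL2016, about the latest that allows 6 months of enrollment, leaves 184 days. The maximum windows are:

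- 2013 index: 3.0-4.0 years
- 2014 index: 2.0-3.0 years
- 2015 index: 1.0-2.0 years
- first half of 2016: 0.5-1.0 year

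The extremes differ about 8-fold.

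**Illustration, with assumed rates that are not in the documents.** Let p6 = 33% be the share starting by month 6, h the annual initiation hazard afterwards (2, 5, 10 or 20%), and m = 8% the annual exit hazard (death or disenrollment). The starting process is the same in every group, so the true odds ratio is 1.00. Index dates are uniform within each period. With k = h + m, and windows running from u to v years beyond month 6:

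P(ever) = p6 + (1 − p6) × (h/k) × [1 − (e^(−ku) − e^(−kv)) / (k(v − u))]

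Worked case, h = 10%, so k = 0.18 and h/k = 0.5556:

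- 2013 index (u = 2.5, v = 3.5): bracket = 1 − (0.6376 − 0.5326)/0.18 = 0.4165; P = 0.33 + 0.67 × 0.5556 × 0.4165 = 0.485.
- First half of 2016 (u = 0, v = 0.5): bracket = 1 − (1 − 0.9139)/0.09 = 0.0437; P = 0.33 + 0.67 × 0.5556 × 0.0437 = 0.346.
- OR, 2016 versus 2013 = (0.346/0.654)/(0.485/0.515) = 0.56.

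The last two columns compare a marker that triples exit (m = 24% versus 8%, exit taken as mortality) and has no effect on starting.

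| Later initiation per year | P(ever), 2013 | P(ever), 2016 | OR 2016 vs 2013 | Marker OR, all index dates | Marker OR, 2013 index only |
|---|---|---|---|---|---|
| 2% | 0.365 | 0.333 | 0.87 | 0.99 | 0.97 |
| 5% | 0.413 | 0.338 | 0.73 | 0.97 | 0.94 |
| 10% | 0.485 | 0.346 | 0.56 | 0.94 | 0.89 |
| 20% | 0.601 | 0.362 | 0.38 | 0.91 | 0.82 |

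**Other assumptions.** With p6 = 35-55%, h = 3-20% per year and 5% exit, the odds ratio for 2013 versus the first half of 2016 is 1.14 to 2.69, which is 0.88 to 0.37 when inverted. Exit of 15% or 30% versus 5% per year gives 0.99 to 0.87 pooled and 0.98 to 0.74 within the 2013 index year.

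**After the change.** With status fixed as any OAC claim within 6 months of index, both groups have P = p6, so the odds ratio is 1.00 whatever the index date or later exit rate.

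**The case against.** The strongest reply is that index year is already a candidate covariate. It is a coarse proxy for the administrative window, and a strong mechanical effect would probably keep it in a stepwise model on a large Medicare sample. It would then absorb much of the window difference for the other predictors. That stands, and it confines the main damage to the percentages and the index-year coefficient. It is not a full answer. Index year is not forced in, its own odds ratio stays uninterpretable as a trend, and it does not deal with death or disenrollment after month 6.

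Second, ever versus never treated is the stated objective, so a 6-month outcome changes the question. That is fair, and is why the ever/never percentages should stay as a description. But a percentage with no horizon is hard to use under any wording of the objective.

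Third, the sizes rest on rates the documents do not give, and they shrink as late starting becomes rare. Also true. In addition, Figure 1 is not reproduced in the copy reviewed and may show the primary window, although the text sets no limit other than 31 December 2016.

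A reader might infer that all the predictor odds ratios mainly measure observation time and survival, or that a real uptake trend will be reversed. The documents do not support either. The survival part is small to moderate under the assumed rates, and the 6-month rule already removes the earliest exits. No true trend is given or was modelled, so reversal is possible but not shown. The DOAC versus warfarin contrast compares two treated groups and is not directly affected.

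**Conclusion.** The point holds for the treated and never-treated percentages and for the index-year odds ratio in the three contrasts against never-treated. The 6-month to 4-year spread follows from the protocol's own dates. The size depends on late initiation: under the assumed rates, the spurious odds ratio for 2016 versus 2013 runs from about 0.87 at 2% per year to 0.38 at 20%. It approaches 1 only if almost nobody starts after month 6. For predictors of mortality the bias is secondary: about 0.99 to 0.91 over all index dates and 0.97 to 0.82 within the 2013 index year for a tripling of mortality. Retaining index year would protect the other predictors from much of the administrative part, but the plan does not guarantee its retention. The planned checks on differential follow-up and competing death do not reach the primary objective.

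**What to change.** For the three contrasts against never-treated and their age and CHA₂DS₂-VASc subgroups, define treatment status, for both the proportions and the logistic model, as a first OAC claim within 6 months of index. Every included patient already has that window. Alternatively, model time to initiation, censored at disenrollment and 31 December 2016, with death as a competing event. Report later starting as cumulative incidence, and keep the ever/never percentages as a descriptive result with the follow-up stated.

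The cost is wording and one derived variable; no new data are needed. Under the 6-month definition, patients who start after month 6 count as not treated by 6 months, and the report should say so. The 6-month definition does not remove the separate conditioning on 6 months of enrollment, with no stated exception for death; that should be listed as a limitation.
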